For quality improvement and future modification and adoption of the multi-component vaping cessation program, we will conduct an exit interview (n=8-12; n=2-3 from each arm based on first available participants) via a video call, with participants to identify the feasibility, facilitators, and barriers of implementing the proposed interventions. Participant who have completed the end-of-study assessment will be contacted by research staff for their willingness to participate in the exit interview. The interview will take place after the Week 12 visit based on participant's availability via a zoom meeting. Therefore, the total participating time in the study is roughly 14-16 weeks. The interview will be audio-recorded and transcribed in order to produce an accurate transcript of the discussion. Each participant in the exit interview will receive a \$25.00 giftcard. The interview will last less than 30 minutes.

Participant enrollment process

Interested potential participants will complete an online screen survey (RedCap link embedded in the recruitment email; and less than 5 minutes to complete), to determine their eligibility based on the inclusion and exclusion criteria. Once potential participants have been deemed as eligible through screening questions, participants will be asked if they would like to participate. If they agree, they will be asked to indicated the times and days that participants would be available to attend the in-person session to complete the informed consent, intake process, including providing saliva sample, urine sample (only for 20 participants who volunteer to be in the biomarker measurement group), and completing the baseline survey (less than 20 minutes to complete), consisting of demographic information, vaping history, vaping experience/behavior, exposure to Tobacco Marketing and Marketing Influences, social efficacy, UPPS impulsive behavior scale, money choice question, and nicotine dependence index (Penn State Cigarette Dependence Index). After completing all the tasks at the baseline session, a randomization algorithm will be utilized to decide which interventions (*Active control, Media literacy, financial incentive, and Combined*) that a participant will be assigned to.

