Participants will complete their first and last saliva cotinine samples in-person during the baseline and final visits. Meanwhile, participants will also download the This is Quitting app at the baseline visit and set up the account with the target quit date (not later than 30 days from the baseline visits). For the remaining check-in sessions (i.e., scheduled live video calls which are mainly for remote saliva sample submissions- a total of three submissions), participants will be instructed during live video call on how to complete the saliva cotinine sample submission with the following procedures.

- Participants will open the new, labeled packaging for each testing kit while on the video call to ensure they are using a new test each time
- Participants will be asked to write down the participants id, test number, date, and time on the test kit
- Participants will take a picture, including participant id, test number, date, and time for verifying the final results and provide the final results and picture to the research staff before ending the call (approximately 10-minute processing time)

The study period consists of an 1-month quitting preparation phase followed by a 2-month abstinence phase. There will be 3 check-in video calls (and thus 3 remote saliva sample submission) for all participants. At each video call, participants will follow the above

instruction to submit a saliva cotinine sample. Each remote video call will take no longer than 20 minutes.

Live, synchronous video calls will be scheduled based on the assigned intervention groups for the next two months for check-in and to submit a remote saliva cotinine sample as described above. For the 1-month quitting preparation phase, participants will be instructed to complete media literacy education lessons (only for participants who are assigned to *Media literacy* and *Combined arms*) and the registration of the text-messaging program (i.e., This is Quitting) and will be instructed not to quit but begin preparing for quitting. They will also be familiar themselves with the remote saliva cotinine sample submission process.

For the participants who are volunteer to be at the biomarker measurement group for providing urine samples (n=20), they will be given instructions on where and how to provide a urine sample to test for five classes of biomarker levels as described above.

Survey instrument

1. Screening survey

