2. Baseline and end-of-study survey, including demographic, vaping history, vaping experience/behavior, attempt to quit, Penn State Nicotine Dependence Index, exposure to Tobacco Marketing and Marketing Influences, UPPS impulsive behavior scale, money choice question, and self-efficacy about not to vape, and wheezing and related respiratory symptoms

Primary outcome

- **biochemically verified vaping abstinence** (negative results- will be cut-off < 30 ng/mL⁷¹), measured by saliva cotinine samples at the Week 12 visit.

Secondary outcome

1. Nicotine abstinence: bi-weekly/monthly saliva nicotine abstinence results (positive vs. negative) will be obtained using the iScreen test kit ([https://stat-technologies.com/product/alere-iscreen-for-cotinine/#:~:text=The%20Alere%20iScreen%C2%AE%20OFD,nicotine\)%20in%20human%20oral%20fluid.](https://stat-technologies.com/product/alere-iscreen-for-cotinine/#:~:text=The%20Alere%20iScreen%C2%AE%20OFD,nicotine)%20in%20human%20oral%20fluid.)) after the target quit date for 2 month in addition to baseline and Week 12 saliva cotinine samples. Saliva sample/results will be collect in person at baseline and Week 12 visits and remotely via live video calls during the abstinence phase. The remote saliva sample collection will follow the instruction below:

- Participants will open the new, labeled packaging for each testing kit while on the video call to ensure they are using a new test each time
- Participants will be asked to write down the participants id, test number, date, and time on the test kit
- Participants will take a picture, including participant id, test number, date, and time for verifying the final results and provide the final results and picture to the research

staff before ending the call (approximately 10-minute processing time) All participant will need to provide a saliva sample at the in-person baseline and the Week 12 visits and at remote video calls (Week 6, Week 8, and Week 10).

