2. Biomarkers of toxic exposures: Twenty participants who are assigned the biomarker measurement group will need to provide the urine sample at the in-person baseline (Week 0) and Week 12) visits at the UNMC clinical research center (CRC). The nurse research coordinator at CRC would assist with the urine sample collection. The biomarker classes may include: 1) cotinine and hydroxycotinine, and 2) creatinine. The biomarker testing of toxic exposure is solely for research purpose and thus the results will not be share with the participants.

3. Engagement, assessed by: a) proportions of media literacy e-learning lessons completed at the end of the quitting preparation phase (Week 4), and b) proportions of participants who submitted the remote saliva cotinine sample at each scheduled time-point at Week 12;

4. Nicotine dependence index, measured by the Penn State E-cigarette Dependence (PSECD) index at baseline and Week 12;

5. Media literacy, measured by the vaping media literary scale at baseline and Week 12.

4) Self-reported vaping abstinence, assessed by the question In the past 30 days, did you vape at all, even a puff of someone else? at Week 12.

Exploratory outcomes

We will collect intervention cost data using all program invoices related to program implementation and survey questionnaire to estimate the cost-effectiveness of the program. For example, we will calculate the incremental cost per additional completing the vaping cessation program, the incremental cost per additional abstinence case across study arms.

C. Select any of the following that apply to the research:

Phase I study

♦ Randomization

Placebo (or non-treatment arm)

Washout

Sensitive surveys or questionnaires

None of the above

Option chosen: Randomization

Describe randomization process and schedule

Participants will be assigned following a randomization table created by the study statistician after completing the consent process and baseline survey on the REDCap platform. To

ensure an even distribution of participants between the four intervention groups, eligible subjects will be randomly assigned to one of four intervention groups using a computer generated randomization table created by the study statistician. We will recruit 5 participants from each intervention group (until fulfilled) for the biomarker measurement group.

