E. Describe briefly the statistical methods used to analyze the data (or reference the appropriate section of the detailed protocol or grant).

Summary statistics will be reported for all participants and further stratified by each group. Group difference will be compared using chi-square test for categorical variables and ANOVA test for continuous variables. Multivariable regression analysis will be performed to compare the intervention effects, adjusted by age, gender, race/ethnicity. Statistical analysis will be performed using STATA 16.0 (College Station, TX) with $p < 0.05$ to be significant.

F. Does this study involve the collection of blood, urine, saliva or other human biological material (HBM)?

Yes

1. Does this research involve genetic testing including Genome Wide Association Studies (GWAS), Whole Genome Sequencing (WGS) or Whole Exome Sequencing (WES)?

No

G. Does this study involve the creation of a tissue bank for future unspecified research? This includes un-used (excess) blood, urine, or tissue, obtained for clinical indication or for research, or additional human biological material collected specifically for future research.

No

DRUGS, BIOLOGIC DRUGS AND DEVICES

13. Drugs and Biologic Drugs

1. Does this research involve the use of drugs or biologics?

No

14. Devices

1. Does this research involve a medical device(s) (including an in vitro device [IVD] (assay), and medical software)?

Yes

A. Check all that apply:

- FDA approved (or cleared) device
- FDA unapproved device
- ♦ In Vitro Device (IVD)

Option chosen: In Vitro Device (IVD)

1. Is the IVD 1) in the laboratory research phase of development, 2) not represented as an effective in vitro diagnostic product and 3) labeled with: "For Research Use Only. Not for use in diagnostic procedures."

No

Option chosen: In Vitro Device (IVD)

a. Is the IVD being shipped or delivered for product testing prior to full commercial marketing and labeled with "For Investigational Use Only. The performance characteristics of this product have not been established."

No

Option chosen: In Vitro Device (IVD)

2. Is the IVD being used in a diagnostic procedure without confirmation of the diagnosis by another, medically established diagnostic product or procedure?

No

Option chosen: In Vitro Device (IVD)

3. Is the IVD (a) invasive, or does it (b) require an invasive sampling procedure that presents significant risk; or does it (c) by design or intention introduce energy into a subject?

No

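### Section 12.E leaves the baseline PSECD and media literacy scores out of the model: specify ANCOVA, and report Week 12 abstinence by baseline cotinine status

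*Combined protocol and SAP*

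**What the plan says.** **Analysis.** Section 12.E plans summary statistics overall and by group, chi-square and ANOVA tests, and one regression: "Multivariable regression analysis will be performed to compare the intervention effects, adjusted by age, gender, race/ethnicity". It does not say whether the continuous outcomes are analysed as Week 12 scores or as changes. No other section fills this in.

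**Scales.** Under Secondary outcome in section 12.B, nicotine dependence is "measured by the Penn State E-cigarette Dependence (PSECD) index at baseline and Week 12" and media literacy is "measured by the vaping media literary scale at baseline and Week 12".

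**Order of events.** Section 12.B, Participant enrollment process, places allocation after the baseline measurements: "After completing all the tasks at the baseline session, a randomization algorithm will be utilized to decide which interventions". Section 12.C agrees.

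**Instrument names.** The baseline survey in the enrollment text includes "money choice question, and nicotine dependence index (Penn State Cigarette Dependence Index". The Survey instrument list, which covers both visits, has "attempt to quit, Penn State Nicotine Dependence Index, exposure to Tobacco Marketing and Marketing Influences, UPPS impulsive behavior scale, money choice question". The secondary outcome is the PSECD. Neither survey list names the media literacy scale.

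**Abstinence.** The primary outcome is a saliva cotinine below 30 ng/mL, "measured by saliva cotinine samples at the Week 12 visit". Section 9 bases entry on self-reported e-cigarette use in the past 30 days together with age, access and interest in quitting. Screening (section 25) is by questionnaire. Baseline cotinine is collected from everyone (section 12.B, Measurement): "Participants will complete their first and last saliva cotinine samples in-person during the baseline and final visits".

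**The concern.** There are two separate matters.

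First, the covariate list is explicit and leaves out what is usually the strongest predictor of a Week 12 score, namely the same score at baseline. Because that score is taken before allocation, it is a legitimate covariate. With 20 per arm and no sample size basis beyond a pilot rule of thumb, intervals will be wide, and estimates for planning a larger trial are the main product. It is also unsettled whether Week 12 scores or changes will be compared, and that choice is better made before the data are seen.

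Second, the primary outcome does not depend on a positive test at entry. Someone who vapes rarely, or without nicotine, could be below the cut-off at baseline, still be below it at Week 12, and count as a success. Without results by baseline status, a reader cannot tell quitting from never having tested positive.

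**Working it through.** **Inputs from the protocol.** Four arms of 20 (section 4); 4 x 20 = 80 reproduces the stated total. The covariates are age, gender and race/ethnicity (12.E). The protocol gives no SD, correlation, abstinence rate or baseline-negative share, so all of these are assumed below.

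**1. ANCOVA against raw Week 12 scores.** Let r be the baseline/Week 12 correlation. ANCOVA multiplies the residual variance by 1 - r², so the CI narrows by 1 - sqrt(1 - r²):

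- r = 0.3: 1 - sqrt(0.91) = 4.6%
- r = 0.5: 1 - sqrt(0.75) = 13.4%
- r = 0.7: 1 - sqrt(0.51) = 28.6%

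These large-sample figures ignore the cost of estimating one more coefficient. A simulation allows for it: 5,000 trials per scenario, normal scores, equal SDs at both visits, no arm effect, and the planned covariates in every model with an assumed 60/15/15/10% race/ethnicity split. Mean 95% CI half-widths at 20 per arm, in SD units:

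| r | raw Week 12 | change | ANCOVA | ANCOVA vs raw | ANCOVA vs change |
|---|---|---|---|---|---|
| 0 | 0.650 | 0.919 | 0.655 | 0.7% wider | - |
| 0.3 | 0.651 | 0.770 | 0.625 | 4% narrower | 19% narrower |
| 0.5 | 0.650 | 0.650 | 0.567 | 13% narrower | 13% narrower |
| 0.7 | 0.651 | 0.505 | 0.469 | 28% narrower | 7% narrower |

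With only 14 per arm analysed, the gains against raw scores are 3.5%, 12.4% and 27.6%, and the cost at r = 0 is about 1%.

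**2. ANCOVA against change scores.** Let k be the Week 12 SD divided by the baseline SD. In units of the baseline variance, the change score has variance 1 + k² - 2rk and ANCOVA has k²(1 - r²). The difference is (1 - rk)², so the gain vanishes when rk = 1. The last column of the table therefore holds only for k = 1. Large-sample narrowing for other values:

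| r | k = 1.4 | k = 1 | k = 0.7 |
|---|---|---|---|
| 0.3 | 8% | 19% | 35% |
| 0.5 | 3% | 13% | 32% |
| 0.7 | 0% | 8% | 30% |

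For example, at r = 0.7 and k = 1.4, rk = 0.98 and the difference is 0.0004 against an ANCOVA variance of 0.9996. The gains against raw scores do not depend on k.

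**3. Baseline-negative participants among those counted abstinent.** Let f be the share negative at baseline, pn their chance of testing negative at Week 12, and pp the same chance for everyone else. The share is f·pn / [f·pn + (1 - f)·pp]. With pn from 0.6 to 1.0 and pp from 0.1 to 0.3:

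- f = 0: 0%
- f = 0.02: 0.012/0.306 = 4% to 0.020/0.118 = 17%
- f = 0.05: 0.030/0.315 = 10% to 0.050/0.145 = 34%, or about 10-35%
- f = 0.10: 0.060/0.330 = 18% to 0.100/0.190 = 53%

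**4. Precision lost by restricting to baseline-positives.** For two arms at an assumed 20% abstinence, the half-width is 1.96 x sqrt(2 x 0.2 x 0.8/m). It is 24.8 points at m = 20, 25.4 at m = 19 (f = 0.05) and 26.1 at m = 18 (f = 0.10).

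**The case against.** Section 12.E answers a form prompt for a brief description, the trial is a feasibility pilot, and both scales are secondary outcomes. The unadjusted analysis is valid, nothing in the text is contradictory on this point, and the sample size does not change. All of that stands, and it keeps the priority low. It does not remove the point, because the covariate list is specific and a better one is available at almost no cost.

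Baseline cotinine is also partly covered. Secondary outcome 1 refers to the baseline sample, and 12.E promises summaries by group, so the baseline-negative count per arm could already be reported. Self-reported 30-day abstinence at Week 12 adds context, screening asks about vaping frequency, and entrants must want to quit. What is still missing is abstinence cross-tabulated by baseline status.

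A reader might infer from the three instrument names, and from the absence of the media literacy scale in the survey lists, that the dependence instrument changes between visits or that a scale has no baseline. The protocol does not support this. The secondary outcomes state that both scales are measured at both visits. The Survey instrument section gives one list for both surveys and presents its items as inclusions, not as a complete set. This is loose wording to be reconciled, not evidence of missing data.

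**Conclusion.** The point holds as a low-priority improvement. It concerns precision and interpretation; it does not show bias.

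Against raw Week 12 scores, ANCOVA is worth about 4% to 28% of CI width over correlations of 0.3 to 0.7, and costs about 1% if the correlation is zero. Against change scores, 19%, 13% and 7% apply only if the SDs are equal at both visits. The gain is about zero when r times the SD ratio is near 1, so a uniform advantage over change scores should not be claimed.

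For abstinence, the protocol allows a baseline-negative participant to count as a success but gives no indication of how many there will be. A reader might take the 10-35% as an estimate of misclassified successes; it is only what would follow from an assumed 5% baseline-negative share and the assumed Week 12 rates. If everyone tests positive at baseline, the primary result is unaffected.

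**What to change.** 1. Add to section 12.E: *Week 12 PSECD and media literacy scores will each be analysed by ANCOVA with terms for arm, the baseline score on the same scale, age, gender and race/ethnicity.*
2. Use one name for the dependence instrument in the enrollment text, the Survey instrument list and the secondary outcomes, and list the media literacy scale in the survey content.
3. Report Week 12 abstinence descriptively by arm and baseline saliva cotinine status, as counts with confidence intervals and without a subgroup test.
4. Repeat the primary comparison in baseline-positive participants as a sensitivity analysis. The all-randomised result stays primary.

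The cost is a few sentences, one extra degree of freedom per scale model and one extra table. The data are already planned: both scales at both visits, and baseline cotinine from everyone. The sample size does not change.
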